Treatment will take place over 12-24 weeks through telemedicine technology (video-conferencing) which, given recent changes in Texas legislation, provides a sustainable platform for disseminating services to those in underserved areas. Treatment begins with psychoeducation about childhood anxiety and how parenting behaviors can contribute to the development and maintenance of anxiety. Subsequently, each week, parents learn tools to increase supportive communication that conveys a message of support (i.e., that they understand and accept their child's distress) and encouragement (i.e., that they are confident in their children's ability to cope). One core aspect of treatment will be parents identifying and steadily reducing specific accommodation behaviors. For example, parents who routinely speak for their child at family gatherings due to their child's social anxiety may tell their child they do not plan on answering questions directed to their child from specific family members, and subsequently resist providing answers when their child is asked questions. Alternatively, parents of children with separation anxiety who usually accompany them on trips outside the house may go on incrementally longer errands while the child is safe at home. These exercises serve as parent-led exposures, the key component of therapy for anxiety.

All relevant information regarding parent-led exercises will be detailed in the treatment manuals/parent-directed books. Therapists will review progress with parents during video-conferencing sessions.

Families will be randomized in a 1:1 ratio into either the low therapist contact bibliotherapy SPACE group or the standard SPACE group. Treatment will be guided by a licensed psychologist/therapist or trainee under the supervision of a licensed psychologist. All treatment will be provided via Zoom, which is HIPAA compliant and secure video-conferencing software.

In addition to posttreatment assessments at the end of the 12-week protocol, a one-month follow-up will assess the sustainability of improvement over a short period. Participants in the low therapist contact bibliotherapy SPACE group who do not reach treatment responder status as assessed at the one-month follow-up will be invited to receive up to additional 8 additional weekly sessions of standard SPACE treatment.

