**LOW THERAPIST CONTACT BIBLIOTHERAPY SPACE GROUP (LTC-SPACE group).** Families randomized to the LTC-SPACE group will receive four 45-minute supportive video calls with a therapist over the first 12 weeks of treatment. Participating families will receive a copy of the book 'Breaking Free of Child Anxiety and OCD' to use at home and in-session with the therapist. During each of the four video-conferencing sessions, therapists will serve to provide encouragement and support as the parent works through the program independently, consistent with previous bibliotherapy research (Rapee et al., 2008) and our ongoing work with parent-led bibliotherapy interventions. Treatment-responder status will be determined based on the 1-month follow up assessment (described below), and treatment non-responders will be offered the chance to receive up to eight additional sessions of standard SPACE treatment. Treatment responders will not receive this additional treatment.

**STANDARD SPACE GROUP.** Families randomized to the standard SPACE group will receive twelve parent-only, once-weekly, 60-minute video calls with a therapist. During each of the twelve videoconferencing sessions, therapists will guide the parent through the implementation of the program, including providing psychoeducation, discussing and practicing supportive communication, identifying accommodation behaviors, and developing weekly goals related to reducing accommodation. Participants in this group will not be offered an additional 8-week course of standard SPACE regardless of treatment-responder status determined at the 1-month follow up assessment.

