**ASSESSMENTS.** All participants will be asked to cooperate in assessments that will occur at pre-treatment (baseline before treatment), post-treatment (at the end of the twelve weeks), and 1-month follow up (4 weeks after first 12 weeks of treatment have concluded). Non-responders to bibliotherapy (assessed at 1-month follow-up) who choose to participate in therapist-led SPACE will complete an additional post-treatment assessment following up to eight additional sessions of SPACE (up to 8 weeks later). The three assessments include a battery of questionnaires and measures at these three timepoints. Depending on group assignment (LTC-SPACE or standard SPACE), measures will also be completed at session visits. Treatment responder status will be assessed at the 1-month follow up, and whether participants in the LTC-SPACE group receive up to 8 additional weeks of standard SPACE will be determined based on the 1-month follow up assessment.

The IE will be an experienced clinician, trained professional, or advanced graduate trainee (supervised by a clinician). The measures that will be administered will include both IE-rated and participant-rated scales (please see attachment in section S). Measures will be completed either in-person or by secure connection (Zoom) and Qualtrics, to reduce burden.

**TREATMENT FIDELITY/INTEGRITY.** All clinician and assessment sessions, in both conditions, will be audio-recorded or video-recorded (with parent consent). These recordings will be used for research purposes, to monitor ongoing fidelity, to quantify treatment adherence, as well as to assess inter-rater reliability and rater drift. If concerns are noted, the clinician and/or IE will not conduct another assessment until procedures have been reviewed. Clinicians will upload audio and video recordings to a web-secure, HIPAA-compliant storage (Box). Fidelity measures have been developed in our pilot work and adapted for use in this project: [1] The Parent Completion and Effort Rating (PCER); and [2] The Treatment Adherence, Content, and Competence Checklist. We will also use treatment fidelity checklists for each session following Lebowitz et al. (2020).

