### G2. Data Analysis

Provide a description of your plan for data analysis. State the types of comparisons you plan (e.g. comparison of means, comparison of proportions, regressions, analysis of variance). Which is the PRIMARY comparison/analysis? How will the analyses proposed relate to the primary purposes of your study?

Descriptive statistics on all randomized participants will be analyzed and if any key variables (e.g. anxiety severity) differ across groups, they will be controlled for in analytic models via inclusion as a covariate. Violations of distributional assumptions will be addressed (e.g. robust sandwich estimators and interval smoothing for continuous variables, and exact logistic regression) in the case of sparingly distributed dichotomous dependent variables.

Study Aims 1-4 address pre-post group differences as a result of treatment, statistical moderation of pre-post treatment effects, and evaluation of additional observed change from post-treatment to 1-month follow up. Chi-square analyses will compare dichotomous outcomes (i.e., treatment response rates). Mixed within-between (time by treatment group) analysis of covariance (ANCOVA) will be used to assess pre-post and post-1-month follow up changes in continuous outcomes (i.e., symptom severity). Within-group change on continuous measures from post-treatment to 1-month follow up will be assessed by dependent t-tests for each treatment group. Between group differences in study dropout will be assessed by logistic regression.

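### For PARS and other continuous outcomes, the only between-arm follow-up contrast in G2 is post-to-1-month change, which does not show whether standard SPACE is still better at 1 month

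*Combined protocol and SAP*

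**What the plan says.** Section G2 gives the between-arm model for continuous outcomes in one sentence: "Mixed within-between (time by treatment group) analysis of covariance (ANCOVA) will be used to assess pre-post and post-1-month follow up changes in continuous outcomes". Two intervals are named: baseline to post-treatment, and post-treatment to 1 month. G2 describes the follow-up part as "evaluation of additional observed change from post-treatment to 1-month follow up". The other continuous follow-up analysis is within arms: "Within-group change on continuous measures from post-treatment to 1-month follow up will be assessed by dependent t-tests for each treatment group".

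Baseline score is not a fixed covariate. G2's rule is conditional: "if any key variables (e.g. anxiety severity) differ across groups, they will be controlled for in analytic models via inclusion as a covariate".

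Section F2 gives the purpose of the visit: "a one-month follow-up will assess the sustainability of improvement over a short period". G1 names PARS as a primary outcome alongside CGI-I response. Aim 1 in Section D is the efficacy of standard SPACE relative to the low-contact version.

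For binary outcomes, G2 says "Chi-square analyses will compare dichotomous outcomes (i.e., treatment response rates") and names no visit. F2 says "Treatment responder status will be assessed at the 1-month follow up".

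**The concern.** Neither named interval is baseline to 1 month, and no arm difference at 1 month is listed for a continuous outcome. The one between-arm follow-up contrast starts from post-treatment, where the arms already differ if standard SPACE works better. It answers whether the gap changed, not whether a gap remains.

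The two questions can have answers of opposite sign. If standard SPACE leads clearly at week 12 and still leads, by somewhat less, at 1 month, the planned contrast favours low contact. Reported alone, it could be summarised as low-contact families catching up, while the lasting advantage on PARS has no planned estimate, interval or test. Under F2, low-contact non-responders are offered further SPACE sessions on the strength of the 1-month result. That visit is therefore the last comparison of the arms as randomised before the offer.

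**Working it through.** **The plan's own figures.** G1's 34 dyads per group (24% v 66%, alpha .05, power .95) reproduces with the two-sided pooled formula without continuity correction: [1.960 × √(2 × .45 × .55) + 1.645 × √(.24 × .76 + .66 × .34)]² / .42² = (1.379 + 1.049)² / .1764 = 33.4, rounded up to 34. G1's 16 participants for PARS reproduces with the between-group repeated-measures formula (two measurements, f = .845, r = .33; power .970). Neither figure concerns the follow-up contrast, and neither changes.

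**The contrast.** Let D_post and D_1m be the advantage of standard SPACE at each visit, positive when standard is better. The post-to-1-month time-by-group contrast is C = D_1m − D_post.

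| D_post (SD) | D_1m (SD) | C (SD) | Better arm at 1 month |
|---|---|---|---|
| 0.8 | 0.8 | 0 | standard |
| 0.8 | 0.6 | −0.2 (towards low contact) | standard |
| 0.2 | 0 | −0.2 (towards low contact) | neither |
| 0 | 0 | 0 | neither |

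The same C goes with a retained benefit and with none, so C alone cannot settle which arm is better at 1 month.

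**Inputs for the size.** From G1: 45 dyads per arm, and r = .33, used here as the correlation of baseline with 1-month score. Assumed: SD 1 at each visit, post-to-1-month correlation ρ from .33 to .6, D_post = 0.8, D_1m = 0.6, two-sided alpha .05, complete data.

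**Planned contrast.** SE = √[2 × 2(1 − ρ)/45].
- ρ = .33: √(2.68/45) = .244, and 0.2/.244 = 0.82. Significant in about 13% of trials.
- ρ = .6: √(1.6/45) = .189, and 0.2/.189 = 1.06. Significant in about 18%.

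**Baseline-adjusted difference at 1 month.** SE = √[2(1 − .33²)/45] = √(1.782/45) = .199, and 0.6/.199 = 3.02. Power is about 85%.

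**Full 0.8 SD retained.** C = 0, so the planned test rejects at its nominal 5%. For the 1-month difference, 0.8/.199 = 4.02, and power is about 97%.

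Simulation of 6,000 trials agrees: rejection .126 and .183 for the planned contrast; .843 to .848 for the 1-month difference, or .974 to .977 with 0.8 SD retained.

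**A second illustration, in points.** Assume SD 5, a common correlation of .33 or .60, lower scores better, and means at the three visits of 18, 10, 10 (standard) and 18, 16, 13 (low contact). The planned contrast is 3 points towards low contact, significant in that direction in 68% to 88% of simulated trials. The baseline-adjusted 1-month difference is 3 points towards standard, significant in 84% to 94%.

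**The case against.** The strongest reply is that the planned contrast is the right one for the stated purpose. F2 wants sustainability and G2 wants additional change after post-treatment; efficacy rests on the pre-post comparison, which starts from randomised baseline. This stands in large part. With complete data, each arm difference is a randomised comparison, so their difference validly estimates how the effect changes. A null result when the whole advantage is kept is the correct answer to that question. A reader might infer that the contrast is biased because it starts from a treatment-altered score; the documents do not support that.

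Nor do they support reading the ANCOVA as conditioning on the post-treatment score. G2 describes a mixed model with time as a factor, so the post-treatment score is a level of the outcome. The covariates it mentions are key variables found to differ between groups.

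It is also fair that the 1-month quantity can be recovered: with the same participants, the two planned contrasts sum to the arm difference in change from baseline to 1 month. But no estimate, interval or test of that sum is planned, and dropout breaks the identity. The sum is also less precise. At correlation .33 its SE is √[4(1 − .33)/45] = .244 against .199, and 0.6/.244 = 2.46 gives about 69% power rather than 85%. A single three-visit model would contain the contrast, but G2 does not specify one.

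Finally, misreporting requires the reader to overlook the pre-post result, and F1 calls the study a pilot. Both limit the harm; neither supplies the missing estimate.

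**Conclusion.** The point holds for continuous outcomes, PARS included. G2 plans a valid measure of how the effect changes after week 12 but no measure of which arm is better at 1 month, and the first cannot stand in for the second. Under the assumed 0.8 SD and 0.6 SD advantages, the planned contrast reads 0.2 SD towards low contact while standard SPACE is 0.6 SD better. These effect sizes, the SD and the ρ range are assumptions. The direction of the argument follows from C = D_1m − D_post alone.

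A reader might go further and infer that the arms are never compared at 1 month. The documents do not support that. Response rates are compared between arms by chi-square, and F2 sets responder status at the 1-month visit. G2 ties the chi-square to no visit, so this is a plausible reading rather than a certain one, but it is enough to confine the point to continuous outcomes.

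This is a worthwhile improvement at almost no cost. It does not undermine the pre-post efficacy analysis.

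**What to change.** In G2, analyse the post-treatment and 1-month scores in one model, with baseline score as a fixed covariate and terms for group, visit and group-by-visit. Report the baseline-adjusted arm difference at post-treatment and at 1 month, each with a 95% CI. Keep the group-by-visit contrast as the maintenance analysis, read it alongside the 1-month difference, and state that no conclusion about which arm is better will be drawn from it alone.

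The cost is a few lines of text. Visits, measures and participant numbers are unchanged, and no planned analysis is lost.

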## Section G: Sample Size/Data Analysis

### G1. Sample Size

How many subjects (or specimens, or charts) will be used in this study?

Local: 240      Worldwide: 240

Please indicate why you chose the sample size proposed:

We will enroll 120 parent-child dyads (n = 240 total children and parents), we anticipate 90 dyads will be eligible (n = 180), in order to meet an intent-to-treat sample size of 45 parent-child dyads per group, accounting for screen-fail rates. This exceeds our anticipated needs of 34 parent-child dyads per group to detect statistical significance in response rates on the CGI-I, the primary outcome measure. The power analysis assumed  $\alpha = .05$ , power = .95, as well as a 24% response rate for the parent self-guided intervention (based on our previous work with a similar approach; Storch et al., under review) and a 66% response rate for individual SPACE based on the Lebowitz et al. (2020) trial. We also anticipate the target sample size will be more than enough to detect differences in reductions on the Pediatric Anxiety Rating Scale (PARS), our other primary outcome, based on the Lebowitz et al. (2020) trial and our own preliminary analysis (Storch et al., under review). For this outcome, we anticipate needing 16 participants to detect statistically significant differences. This assumes an effect size of  $f = .845$ ,  $\alpha = .05$ , power = .95, and a correlation among repeated measures of  $r = .33$ .

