## **Section L: Cost/Payment**

Delineate clinical procedures from research procedures. Will subject's insurance (or subject) be responsible for research related costs? If so state for which items subject's insurance (or subject) will be responsible (surgery, device, drugs, etc). If appropriate, discuss the availability of financial counseling.

Participants will receive free treatment but will not be compensated otherwise. Neither subjects nor subjects' insurance will be responsible for research related costs.

If subjects will be paid (money, gift certificates, coupons, etc.) to participate in this research project, please note the total dollar amount (or dollar value amount) and distribution plan (one payment, pro-rated payment, paid upon completion, etc) of the payment.

Dollar Amount:

0

Distribution Plan:

N/A

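### The unpaid 1-month visit is the only route to extra therapy, and only for LTC-SPACE non-responders; G2 compares dropout by arm alone, so selective attendance could modestly bias the 1-month comparison

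*Combined protocol and SAP*

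**What the plan says.** Section F2 (Treatment) says that LTC-SPACE families "who do not reach treatment responder status as assessed at the one-month follow-up will be invited to receive" up to eight further weekly sessions of standard SPACE. LTC responders get none. For the standard arm: "Participants in this group will not be offered an additional 8-week course of standard SPACE regardless of treatment-responder status". F2 (Assessments) makes the 1-month assessment the basis for this decision, and families who take the sessions have one more assessment afterwards.

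Section L: "Participants will receive free treatment but will not be compensated otherwise"; the payment amount is 0.

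G2 compares response rates by chi-square, continuous outcomes by a mixed time-by-group ANCOVA (pre to post, and post to 1 month), and within-arm change from post to 1 month by dependent t-tests. Its only statement on attrition is "Between group differences in study dropout will be assessed by logistic regression". It names no predictor besides group, no time window, no missing-data method and no sensitivity analysis. G1 refers to an intent-to-treat sample of 45 dyads per group. The reduction from 120 to 90 dyads allows for screen failures, not for loss after randomization.

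**The concern.** Four groups of families face the 1-month visit: responders and non-responders in each arm. The protocol gives one of them, the LTC non-responders, a concrete reason to attend. If they attend more often than LTC responders, the response rate among LTC attenders falls below the true rate. Nothing in the offer produces a matching shift in the standard arm, so the difference between arms is biased.

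A comparison of dropout by arm is a weak guard, because the bias comes from the mix of families who attend and not from the total.

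The post-to-1-month ANCOVA and the t-tests depend on this visit. The primary chi-square may depend on it too: G1 makes CGI-I response a primary outcome, F2 determines responder status at 1 month, and neither G1 nor G2 gives the chi-square a time point.

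**Working it through.** **Inputs from the documents.** Response is 66% for standard SPACE and, from G1, a "24% response rate for the parent self-guided intervention". Alpha is .05, power .95, allocation 1:1, with 45 dyads per arm. The documents give no attendance or dropout rate, so every attendance figure below is an assumption.

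**The plan's own figure.** Two-sided chi-square with pooled variance, mean rate 0.45:

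n = [1.96·√(2·0.45·0.55) + 1.645·√(0.24·0.76 + 0.66·0.34)]² / 0.42² = (1.379 + 1.049)² / 0.1764 ≈ 33.4, rounded up to 34.

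This matches G1's 34 per group (power 95.3%). The sample size is not in dispute.

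**Formula.** With true response p, and attendance a_R for responders and a_N for non-responders, the response seen among attenders is p·a_R / [p·a_R + (1−p)·a_N].

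**Incentive only.** Everyone attends at a base rate except LTC non-responders, who attend more. The standard arm is then unbiased.

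| True response (standard / LTC) | Base rate / LTC non-responders | LTC response seen | Overstatement | Dropout, standard / LTC |
|---|---|---|---|---|
| 66% / 24% | 85% / 90% | 0.204/0.888 = 23.0% | 1.0 point | 15.0% / 11.2% |
| 66% / 24% | 75% / 95% | 0.180/0.902 = 20.0% | 4.0 points | 25.0% / 9.8% |
| 45% / 45% | 85% / 90% | 0.3825/0.8775 = 43.6% | 1.4 points | 15.0% / 12.3% |
| 45% / 45% | 75% / 95% | 0.3375/0.860 = 39.2% | 5.8 points | 25.0% / 14.0% |

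In simulated trials with 45 per arm (Pearson chi-square), the two rows with no true difference give type I error of about 5% and 8%. Across the four rows the arm-level dropout test is significant in roughly 7% to 50% of trials.

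**If other groups are also lost selectively.**
- At 66% versus 24%, with attendance (responders/non-responders) of 85/75 in standard SPACE and 61/88 in LTC: standard 0.561/0.816 = 68.8%, LTC 0.1464/0.8152 = 18.0%. The gap is 51 points instead of 42, with dropout of 18.4% and 18.5%.
- At 45% in both arms, with 85/75 and 70/95: 0.3825/0.795 = 48.1% against 0.315/0.8375 = 37.6%. The spurious gap is 10.5 points and false rejection is about 15%.
- Making standard-arm attendance unrelated to outcome, at the same total, reduces these to 48 points and to 7.4 points (about 10% false rejection).

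**If disappointed LTC non-responders leave.** With 70% of them attending and 80% of everyone else, LTC response seen is 0.192/(0.192 + 0.532) = 26.5%. The gap is 39.5 points, so the advantage of standard SPACE is understated by 2.5 points.

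**The case against.** The strongest reply is that the offer alone does not produce a large, hidden bias, and that is right. LTC responders and all standard-arm families have the same absence of incentive, so nothing in the protocol explains why LTC responders should attend far less than standard responders, or why standard-arm non-responders should be lost. The patterns giving 9 to 10 points need one or both. An incentive that brings in LTC non-responders also lowers total LTC dropout, so the arm-level test will sometimes flag it.

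The direction is also conditional. Families must know the rule before the visit. The consent form is not available here, and the Section R advertisement mentions three assessments but no extra sessions. Remote assessment may also keep attendance high.

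On scope, G2 presents the 1-month data as change beyond the pre-post comparison, and week 12 comes before the offer is decided. G1 mentions an intent-to-treat sample, although it does not say how absent families enter the analysis.

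A reader might also infer that the dropout regression is tilted against LTC, because families who accept extra sessions stay under observation up to 8 weeks longer. The documents do not support that. The sessions are optional, G2 names no analysis of that period, and nothing says that leaving them counts as study dropout. The term is undefined, which calls only for a clarification.

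What remains is that the documents build in an unequal incentive at a visit they analyse, and name no method that addresses it.

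**Conclusion.** The point holds as a modest risk, not a demonstrated bias. If families know of the offer and only the incentive operates, the 1-month advantage of standard SPACE is overstated by about 1 to 4 points at the G1 response rates. With no true difference the spurious gap is 1.4 to 5.8 points and type I error about 5% to 8%. These figures assume attendance of 75–85% generally, 90–95% among LTC non-responders, and analysis of attenders only, which G2 neither states nor rules out.

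An effect of about 9 to 10 points, with up to about 15% false rejection, needs further selective loss that the offer does not explain, and the sign can reverse. It would also be too strong to say that the bias must go undetected, or that the primary result is compromised. The dropout test detects the incentive-only pattern unreliably but not never, and whether the primary chi-square uses the 1-month visit is left open. The change is worth making because the data needed are already scheduled and the method is credible only if fixed beforehand.

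**What to change.** In G2:

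1. Estimate 1-month CGI-I response and PARS for all randomized dyads by multiple imputation within arm, using baseline PARS and week-12 CGI-I and PARS. Keep the attenders-only analysis as a sensitivity analysis. Imputation removes the bias only if attendance depends on those data, so add a delta analysis with arm-specific departures from missing at random.
2. Report 1-month attendance by arm and week-12 response. Add week-12 response and its product with arm to the dropout model as a descriptive check. Its power is low at 45 per arm: even if week-12 response matched 1-month response exactly, about 3% to 26% under the incentive-only patterns and about 50% under the two selective-loss patterns. A null result should not be read as reassurance.
3. State that dropout is counted in both arms only up to the 1-month visit, so that leaving the optional extra sessions is not counted in one arm only.

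The cost is a few sentences of SAP text, a little more analysis on data F2 already schedules (taking CGI-I and PARS to be in the battery given at all three assessments), and slightly wider intervals. The offer of extra sessions and the visit schedule are unchanged.
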